8.6 Analysis of Efficacy

8.6.1 Primary Efficacy Variable(s)

The primary efficacy variable is the change from baseline through Week 24 in the score of the Abdominal Symptoms domain of CeD PRO questionnaire.

8.6.1.1 Primary Estimand and Handling of Intercurrent Events

The primary estimand corresponding to the primary efficacy variable consists of the following attributes:

A. Target Population

Adult patients with non-responsive celiac disease who have attempted a gluten free diet for at least 12 months as defined by the inclusion and exclusion criteria in the study protocol.

B. Endpoint

Absolute change from baseline through Week 24 in abdominal symptoms as measured by the Abdominal Symptoms domain of the CeD PRO questionnaire,

C. Population-Level Summary

Overall mean values (averaged across 24 weeks) of each of the 3 PRV-015 treatment groups compared with placebo of the change from baseline in the Abdominal Symptoms domain of the CeD PRO questionnaire.

D. Strategy for Addressing Intercurrent Events

Treatment policy strategy, i.e. all collected primary endpoint data is used regardless of intercurrent events.

Intercurrent events are events which occur after treatment initiation and may interfere with the analysis of the primary endpoint. Intercurrent events are considered to be the following:

- · Intake of prohibited medications
- · Presence of gluten

As per treatment policy strategy intercurrent events are handled by collecting all primary endpoint data following any intercurrent event.

Intercurrent event counts and timings will be summarized by treatment group. Additional analysis may be done to further explore the effect of intercurrent events.

Intake of Prohibited Medication

The number of subjects who have taken at least one prohibited medication after randomization will be tabulated by treatment group.

The time (in weeks) from randomization to the first instance of a prohibited medication will also be summarized by treatment group. This time will be calculated as (start date of first post-randomization prohibited medication – randomization date + 1)/7.

The following medications are considered prohibited medications, even if they were used to treat AEs, as indicated in the study protocol:

 Systemic or intestinal immune suppressants, including steroids. Inhaled or nasal steroids for respiratory diseases such as asthma and allergic rhinitis as well as topical steroids (except intestinal) are permitted.

- Oral pharmaceutical presentations (e.g., capsules) of probiotic supplements. Probiotics in foods (e.g., yogurt) are acceptable.
- Chronic or continuous oral and IV antibiotics (>2 weeks use). Topical antibiotic use is allowed.
- Systemic antiviral medications
- Systemic antifungal medications
- Live vaccines (within 14 days before Study Visit 3)
- Investigational drugs

If such medication was prescribed as needed ("prn") or was taken after Visit 16, it will not be considered as an intercurrent event.

The full list of subjects who have taken a prohibited medication will be identified in a blinded manner prior to database lock and study unblinding.

Absence or Presence of Gluten

Subjects are categorized into Absence or Presence of gluten category based upon having negative stool and urine gluten tests or having positive test result for either stool or urine gluten test, respectively. If both tests are missing or one test is missing and the other one is negative the visit will be missing. If one test is positive and the other one is missing it will be presence. This will be assessed using the nominal visit for urine or stool gluten samples. Positive stool gluten test is defined as the values above $0.156~\mu g$ GIP/g. Positive urine gluten test result is defined as the values above 6.25~ng GIP/ml. Number of subjects with absence or presence of gluten will be tabulated by treatment group. Each subject could be counted in both absence and presence category at different visits.

Month	Month ending visit	Qualifying Absence	Qualifying Presence		
0	Visit 3	Stool and Urine gluten both negative at Visit	gluten positive at		
1	Visit 5	Stool and Urine gluten both negative at Visit 5	Stool or Urine gluten positive at Visit 5		
2	Visit 7	Stool and Urine gluten both negative at Visit 7	gluten positive at		
3	Visit 9	Stool and Urine gluten both			

		negative at Visit 9	
4	Visit 11	Stool and Urine gluten both negative at Visit 11	gluten positive at
5	Visit 13	Stool and Urine gluten both negative at Visit 13	gluten positive at
6	Visit 15	Stool and Urine gluten both negative at Visit 15	gluten positive at

Time (in weeks) from first dose to the first time observing the presence of gluten will also be captured for each subject. This will be calculated as (Visit date corresponding to the first presence of gluten—date of first dose of double-blind treatment + 1)/7.

Subjects having an absence or presence of gluten will be presented in a data listing.

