At the end of the 4-week single-blind, placebo run-in period, subjects will return to the study site for Visit 3 (Week 0/Day 1) and be re-evaluated for inclusion/exclusion criteria. Those who meet the entry criteria at this time will enter the 24-week double-blind treatment period (from Visit 3 to Visit 15). At the same visit, eligible subjects will be randomized in a 1:1:1:1 ratio to receive 100 mg, 300 mg, or 600 mg PRV-015, or matching placebo, subcutaneously (SC) every 2 weeks (q2w). Randomization will be stratified by VH:CD of <2 or ≥ 2 and by the CeD PRO Abdominal Symptoms domain score of <3 or ≥ 3 at baseline using the average of the Abdominal Symptoms domain scores over the last week of the placebo run-in period immediately before randomization. Enrollment of subjects with Marsh score of 0 or 1 will be capped at approximately 72 subjects, although fewer than 72 may be enrolled.

The study drug (1 of the 3 doses of PRV-015 or placebo) will be administered SC q2w in the double-blind treatment period through Visit 14. Each dose will be administered in a double-blind fashion. The subjects' adherence to GFD will be assessed retrospectively throughout the study using the stool and urine gluten tests based on the G12 antibody to interpret possible dietary changes or transgressions. Results will not be communicated to the subjects, who will be instructed to continue their baseline dietary habits throughout the study.

Subjects will be assessed for efficacy and safety throughout the study, as indicated in the Schedule of Activities (SoA) (Section 1.3). Clinical assessments occur from Visit 3 through Visit

16. Safety is also assessed at each on-site visit through the end-of-study visit (Visit 16), which takes place 6 weeks after the last planned dose of the study drug.

Randomized subjects will undergo a second EGD and biopsy at the end of the 24-week treatment period, within 7 days of Visit 15 in order to assess changes from baseline in IELs and VH:CD.

Visits 6, 8, 10, and 12 may be conducted either at the site or remotely by certified mobile personnel per the Investigator's decision.

All subjects enrolled in the study will complete the daily eDiary for CeD PRO (at the end of the subject's daily activities, when no more food will be consumed) and for the stool frequency question from Visit 1 through the end of the study at Visit 16, which will encompass the single-blind placebo run-in and the double-blind treatment period and a safety follow-up period.

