8.6.1.3 Sensitivity Analyses for Primary Model to evaluate missing data imputation methods

The primary model is a linear mixed model assuming data missing at random (MAR). Sensitivity analyses are done to assess the robustness of the primary efficacy analysis results with respect to different methods of handling missing values, under missing not at random (MNAR) assumption.

For the analysis of the primary efficacy endpoint, missing data will be imputed at the week level using Multiple Imputation (MI) after applying the visit windowing strategy for the CeD PRO weekly scores.

The MI will be carried out following 3 steps:

Step 1. Generation of imputed datasets

The PROC MI procedure of the SAS system with MCMC statement will first be used impute intermittent missingness by treatment group in order to generate 100 sets of data with monotone missingness. Subsequently, PROC MI will be used with MNAR statement indicating the neighboring-case missing values (NCMV) method (Molenberghs and Kenward, 2007) in order to impute the monotone missing values to obtain complete data sets. The imputation model will include treatment group, continuous baseline CeD PRO Abdominal Symptoms domain score, VH:CD at baseline, and CeD PRO Abdominal Symptoms weekly domain score at previous time points as covariates.

Step 2. Model-based analysis using each imputed dataset

Each of the 100 imputed datasets will be analyzed using the primary model specified in Section 8.6.1.2.

Step 3. Pooling the results from each model-based analysis

The results from the analysis of each imputed dataset will be combined using Rubin's rule (Rubin, 1987) by implementing the PROC MIANALYZE procedure of the SAS system.

8.6.1.4 Sensitivity Analyses of Primary Model to Evaluate Effect of Intercurrent Events If evaluation of intercurrent events (Section 8.6.1.1) indicates need for analysis of the primary endpoint in the presence of intercurrent events, the primary analysis will be repeated separately in the mITT analysis set addressing each of the following adjustments, after visit windowing is applied for the CeD PRO weekly data:

Prohibited Medication: Data collected prior to first use of prohibited medication will be used as observed. Time points after first use of prohibited medication will first be set to missing. The MI procedure in Section 8.6.1.3 will then be applied.

Presence of Gluten:

For subjects who do not experience presence of gluten per Section 8.6.1.1, all observed data will be used.

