8.6.1.5 Sensitivity Analysis of Primary Model to Evaluate Alternate Baseline Definition

In some instances, randomized patients who needed to be rescheduled for their Visit 3 (e.g., first dose of double-blind treatment) experienced delays between the end of their run-in period and the first dose of double-blind treatment. In this regard, a sensitivity analysis will be conducted for the primary model (Section 8.6.1.2) in the mITT analysis set to use the following baseline definition for the CeD PRO Abdominal symptoms domain:

Average of scores from 7 days prior to the first dose of double-blind treatment.

In some instances, subjects were not compliant with completing the CED PRO questionnaire daily in the week prior to randomization. In this regard, a sensitivity analysis will be conducted for the primary model (Section 8.6.1.2) in the mITT analysis set to use the following baseline definition for the CeD PRO Abdominal symptoms domain:

 Alternative baseline will be defined as the 'Average of scores from 10 days prior to randomization (e.g., last 10 days of placebo run-in)'.

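### Prohibited medication is counted and timed from randomization although intercurrent events are defined from treatment start, and the timing summary in effect covers only subjects who had an event

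*SAP*

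**What the plan says.** SAP 8.6.1.1 gives the general rule: "Intercurrent events are events which occur after treatment initiation and may interfere with the analysis of the primary endpoint". It names two such events, prohibited medication and presence of gluten, and promises that "Intercurrent event counts and timings will be summarized by treatment group".

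The two events then get different time origins.

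- **Prohibited medication.** "The number of subjects who have taken at least one prohibited medication after randomization will be tabulated by treatment group". For timing: "The time (in weeks) from randomization to the first instance of a prohibited medication will also be summarized by treatment group". The formula is (start date − randomization date + 1)/7. Use as needed and use after Visit 16 are left out.
- **Gluten.** "Time (in weeks) from first dose to the first time observing the presence of gluten will also be captured for each subject". The formula is (visit date − first-dose date + 1)/7. The accompanying table starts at Month 0, which is Visit 3.

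Neither formula comes with a value or a censoring date for a subject who never has the event. SAP 8.2.1 sets the default for continuous variables: number non-missing, number missing if above zero, mean, median and so on.

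SAP 8.5 classes a medication that both starts and stops before double-blind treatment as prior, not concomitant.

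SAP 8.6.1.4 repeats the primary analysis with the events removed, if the evaluation under 8.6.1.1 shows a need. For prohibited medication: "Time points after first use of prohibited medication will first be set to missing". Multiple imputation follows.

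Randomization and first dose are planned together at Visit 3 (Protocol 4.1: "At the same visit, eligible subjects will be randomized in a 1:1:1:1 ratio"). SAP 8.6.1.5 records that some randomized patients whose Visit 3 had to be rescheduled "experienced delays between the end of their run-in period and the first dose of double-blind treatment".

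**The concern.** One section defines the event from treatment start and then counts one of its two events from an earlier date. Medication taken and finished before the first double-blind dose cannot be a consequence of treatment, and SAP 8.5 would not call it concomitant. Under 8.6.1.1 it is nevertheless an intercurrent event, and under 8.6.1.4 it would remove that subject's whole post-baseline record.

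The timing summary raises a second question. The time to a first event is undefined for subjects without one, so a mean or median of the available times describes only those who had the event. It does not show how soon events occur in the arm, and it takes no account of unequal follow-up. These counts and timings are the named input to the decision whether to run 8.6.1.4, for which the SAP gives no threshold.

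**Working it through.** The plan states no figure on this point, so there is none to reproduce. The check has two parts.

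**1. Time origin**

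*Can the two dates differ?* By design they do not. In practice they can:

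- The main baseline is the 7 days before randomization (SAP 8.2.2.1, Table 2), and 8.6.1.5 adds a sensitivity baseline of the 7 days before first dose because of rescheduled visits. The two differ only if the dates differ.
- SAP 8.3 also has a disposition row for subjects randomized but not dosed.

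*Illustration (assumed dates).* Randomized day 0, course started day 3 and finished before first dose on day 7.

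- SAP formula: (3 − 0 + 1)/7 = 0.57 weeks, counted as an event.
- Same formula from first dose: (3 − 7 + 1)/7 = −0.43 weeks, so before treatment and not an event under the SAP's own definition.
- SAP 8.5: prior medication.

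With a gap of g days every time shifts by g/7 weeks. With no gap nothing changes.

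*Effect in 8.6.1.4.* The model uses Weeks 2, 4, …, 24, which is 24/2 = 12 time points. All follow the first dose and so also follow use in the gap. Read literally, all 12 are set to missing and imputed.

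*Gluten.* The first-dose origin does not fully settle this event either. A positive Visit 3 test, with dosing on the same day, gives (0 + 1)/7 = 0.14 weeks and enters as a first presence, although the test belongs to the pre-dose visit.

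**2. Timing summary**

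*Inputs.* About 55 subjects per arm (SAP 7) and a 24-week period. Event rates are assumptions, because the documents give none. Base case: 20% of placebo subjects have an event by Week 24, at a constant rate.

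*Formulas.* Rate λ = −ln(1 − p)/24. Mean time among subjects with the event, constant rate: 1/λ − 24(1 − p)/p. Mean event-free time to Week 24 over all subjects: p × (mean among events) + 24(1 − p).

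- **Placebo.** λ = −ln(0.8)/24 = 0.00930. Mean among events 107.55 − 96.00 = 11.6 weeks.
- **Active, risk halved throughout.** p = 1 − √0.8 = 10.6%. Mean 215.11 − 203.33 = 11.8 weeks.
- **Active, rate cut to a quarter from Week 8.** Cumulative hazard 8λ + 16 × 0.25λ = 12λ, so p is again 10.6%. Events before Week 8: 7.17% at mean 3.95 weeks. Events after: 3.39% at mean 15.95 weeks. Overall (0.0717 × 3.95 + 0.0339 × 15.95)/0.1056 = 7.8 weeks.

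| Arm | Subjects with event | Events of 55 | Mean time, events only | Mean event-free time, all subjects |
|---|---|---|---|---|
| Placebo | 20.0% | 11.0 | 11.6 wk | 21.5 wk |
| Active, halved throughout | 10.6% | 5.8 | 11.8 wk | 22.7 wk |
| Active, quarter rate from Week 8 | 10.6% | 5.8 | 7.8 wk | 22.3 wk |

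The two active arms have the same 24-week incidence. The events-only mean puts one level with placebo and the other almost 4 weeks earlier. The count and the all-subject measure rank both active arms as better.

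*Range.* With risk halved throughout, active against placebo is 11.9 against 11.8 weeks at 10% placebo incidence and 11.5 against 11.0 at 40%: no reversal, and almost no signal. With the rate cut to 0, 0.25 or 0.5 of placebo from Week 4, 8 or 12, the better arm's mean is earlier in every case tried, 2.0 to 10.4 weeks against 11.0 to 11.8.

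*Extreme case.* At 2% per week, placebo has events in 1 − e^(−0.48) = 38% of subjects at a mean of 11.0 weeks. If events stop at Week 8 on active, 1 − e^(−0.16) = 15% have one, at a mean of 3.9 weeks.

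**The case against.** The case on the other side is substantial, and most of it stands.

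- A reader might infer that a better arm will look worse in this table. The documents do not support that. Reversal needs a non-proportional pattern such as a delayed effect, which nothing in the plan predicts, and it did not occur when risk was halved throughout. The number of subjects with the event is tabulated by arm beside the times and pointed the right way in every scenario.
- A reader might infer that the primary result is at risk. It is not. The primary estimand is treatment policy and uses all collected data. No event time enters the estimate, the test or the power.
- The SAP does not say that times are summarized over events only. That is an inference from formulas that need an event date, from the absence of a censoring rule, and from the non-missing default in 8.2.1. It is the natural reading, but it is a reading.
- Few subjects can be caught in the gap. Randomization and first dose are planned for one visit, the number and length of delays are not given, as-needed use is excluded, and antibiotics count only beyond two weeks. This limits the size but does not remove the contradiction: the systemic steroid, antiviral, antifungal and oral probiotic entries carry no minimum duration.
- The loss of 12 scores needs such a subject to exist, the conditional analysis to be run, and its text to be applied literally.
- The illustration stops at Week 24, whereas only use after Visit 16 (Week 28) is discarded, so its figures do not forecast the actual table.

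**Conclusion.** The point holds as a minor one, in two parts.

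The time origin is a real internal contradiction. SAP 8.6.1.1 breaks its own definition for prohibited medication, uses a different origin for gluten, and disagrees with SAP 8.5. For a subject whose only prohibited use falls between randomization and a delayed first dose, the consequence is a false intercurrent event and, in the conditional sensitivity analysis read literally, 12 of 12 post-baseline scores replaced by imputation. The number of such subjects is unknown and probably small.

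The timing summary is in effect restricted to subjects with events. It is nearly blind to a constant halving of risk and can reverse under non-proportional rates. These sizes rest on assumed event rates. The accompanying counts limit the harm to a descriptive table and to its part in the decision on 8.6.1.4.

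**What to change.** In SAP 8.6.1.1, and by reference in 8.6.1.4:

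1. Use the first double-blind dose as the time origin for both events.
2. Count prohibited medication as an intercurrent event only if it was taken on or after that dose. Include courses that began earlier and continue past it, and state the event date for them (for example, the date of first dose).
3. Exclude the pre-dose Visit 3 (Month 0) gluten test from the post-treatment events. It can still be shown as a baseline row.
4. Next to the counts, report the Kaplan-Meier cumulative incidence of the first event by arm over all mITT subjects. Censor event-free subjects at their last gluten test (gluten) or last primary-endpoint diary day (medication).

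The cost is a change of SAP wording and two more outputs from data already collected. The primary analysis does not change.

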8.1. All Laboratory Tests

The maximum amount of blood collected from each subject over the duration of the study is expected not to exceed 400 mL over a period of approximately 9 months. This estimation does not include repeat or unscheduled samples, which may be taken for safety reasons or for technical issues with collected samples.

All laboratory tests to be conducted at in-office visits are listed as follows.

Screening Visit (within 28 days before Visit 1)

- Chemistry: calcium, ALT, AST, albumin, total and direct bilirubin, sodium, potassium, blood urea nitrogen (BUN), creatinine, chloride, CO₂, glucose, total protein, alkaline phosphatase (ALP) (if ALP is >3 x ULN, test 5' nucleotidase or GGT), magnesium, phosphorus
- Complete blood count (CBC): hemoglobin, hematocrit, platelets, white blood cell count (WBC) with differential, red blood cell count (RBC), mean corpuscular volume (MCV), mean corpuscular hemoglobin concentration (MCHC), mean cell hemoglobin (MCH)
- Urinalysis (dipstick and microscopic)
- HbA1C (subjects with diagnosed Type 1 or Type 2 diabetes only)
- HLA DQ2/8 (as needed)
- Testing for HIV, HBV and HCV for exclusion as follows:
 - HIV: positive antibody to p24 antigen (Ab-p24Ag) for human immunodeficiency virus (HIV) 1 or 2 confirmed by positive HIV 1/2 Western blot
 - HBV: HBsAg, anti-HBc total (IgM and IgG) confirmed by positive HBV DNA, anti-HBs
 - HCV: HCV antibody confirmed by positive HCV RNA
- IGRA
- *H. pylori* stool test
- Serum pregnancy test (all WOCBP only)
- FSH/LH for women with suspected menopause (i.e., not surgical menopause)
- Serum IgA
- Anti-tTG IgA and IgG, anti-DGP IgA and IgG

Visit 1 (Single-blind run-in Week -4)

- Chemistry (same tests as screening)
- CBC (same tests as screening)
- HbA1C (subjects with diagnosed Type 1 or Type 2 diabetes only)
- Urinalysis (same tests as screening)
- Stool and urine gluten tests
- Urine pregnancy (WOCBP only)

Visit 2 (Single-blind run-in Week -2)

- Stool and urine gluten tests

- Urine pregnancy (WOCBP only)

Visit 3 (Week 0/Day 1)

- Chemistry (same tests as screening)
- CBC (same tests as screening)
- Urinalysis (same tests as screening)
- Stool and urine gluten tests
- Urine pregnancy test (WOCBP only)
- Anti-tTG IgA, anti-DGP IgA
- Ferritin, iron, TIBC, vitamins D, B12, folate
- Serum biomarkers (e.g., IL-15)
- Trough concentration of PRV-015
- ADA

Visit 4 (Week 2/Day 15)

- Stool and urine gluten tests
- Trough concentration of PRV-015
- ADA

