4 STUDY TYPE AND DESIGN

This is a Phase 2b, randomized, double-blind, placebo-controlled, parallel-group study to evaluate the efficacy and safety of PRV-015 in adult patients with NRCD who are on a glutenfree diet (GFD).

After signing the informed consent form (ICF), subjects will undergo screening assessments for the study in a screening period of up to 28 days before Visit 1. The screening assessments will include the collection of demographics, medical history, and past record of the diagnosis of celiac disease, if available. Subjects should demonstrate 1) attempted adherence to a GFD, confirmed by a lack of strong serological positivity (<3.0 x cutoff value for positivity), and 2) exposure to gluten contamination by presenting with detectable serology (above the lower limit of quantitation).

After initial screening, potentially eligible subjects will enter a single-blind, placebo run-in period for 4 weeks, starting at Visit 1. During the run-in period, all subjects will receive subcutaneous (SC) injections of placebo every 2 weeks (q2w), at Visit 1 and Visit 2, in a single-blind fashion, in which the Investigator is aware of the treatment administered but the subjects are not. Subjects will be asked to maintain their current GFD through the entire study and to complete the daily electronic diary (eDiary) for CeD PRO questionnaire as well as a stool frequency question (stools of Type 6 or 7 on Bristol Stool Form Scale [BSFS]). A baseline upper esophagogastroduodenoscopy (EGD) and biopsy will be conducted during the single-blind run-in period. The results will be used to obtain the villous height-to-crypt depth ratio (VH:CD) for randomization stratification.

At the end of the 4-week single-blind, placebo run-in period, subjects will return to the study site for Visit 3 (Week 0/Day 1) and be re-evaluated for inclusion/exclusion criteria. Those who meet the entry criteria at this time will enter the 24-week double-blind treatment period (from Visit 3 to Visit 15). At the same visit, eligible subjects will be randomized in a 1:1:1:1 ratio to

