
For subjects who experience the first presence of gluten, data from the visits prior to the presence of gluten will be used as observed. Once the first presence of gluten is experienced, observed data is only used from later visits if they meet the definition of absence of gluten. Visits exhibiting the presence of gluten will be set to missing and follow a similar multiple imputation procedure as in 8.6.1.3, with the exception that missing data will be imputed using data at those visits from placebo subjects who did not experience a presence of gluten.

Example 1 – Subject does not meet definition of presence – all observed data used

	Visit 3	Visit 5	Visit 7	Visit 9	Visit 11	Visit 13	Visit 15
Gluten Tests	Negative/ Negative	Negative/ Negative	Negative / Negative	Negative / Negative	Negative / Negative	Negative/ Negative	Negative/ Negative
Data used	Observed	Observed	Observed	Observed	Observed	Observed	Observed

Example 2 - Subject meets definition of presence at Visit 7 - imputation using placebo at visit 7

	Visit 3	Visit 5	Visit 7	Visit 9	Visit 11	Visit 13	Visit 15
Gluten	Negative/	Negative/	Positive/	Positive/	Negative/	Negative/	Negative/
Intake Tests	Negative	Negative	Positive	Negative	Positive	Negative	Negative
Data used	Observed	Observed	Presence Impute Visit 7	Presence Impute Visit 9	Presence Impute Visit 11	Observed	Observed

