The Marsh-Oberhuber histology score (M0, M1, M2, M3a, M3b, or M3c) will be assigned from EGD biopsy samples collected at visits 2 and 15. The Marsh-Oberhuber histology scale will be assessed as frequencies and proportions. Frequencies will be tabulated for each category on the scale, along with respective change from baseline in a shift table.

Additionally, a 3-category outcome will be derived, in which subjects are categorized as having worsening scores from baseline, no change from baseline, and those with improvement from baseline. Marsh score of 0 is considered the best and Marsh score of 3c is considered the worst. Any score shifts in the direction from 0 towards 3c (e.g. 0 to 1 or 3a to 3b) is considered worsening. On the other hand, any score shifts from the direction from 3c to 0 is considered as improvement (e.g. 3c to 3b, or 2 to 0 is considered improvement).

The 3-category outcome will be summarized by treatment group. The Cochran–Mantel–Haenszel test (CMH) (using modified ridit scores for the 3-level outcome), stratified by baseline Marsh-Oberhuber score (M0, M1, M2 vs. M3a, M3b, M3c) will be used to assess differences between active and placebo treatments in this 3-category outcome.

Adherence to GFD

The G12 antibody-based stool and urine gluten tests are validated assays used to assess patient compliance with gluten challenge and to measure possible gluten contamination.

The G12 stool test and urine gluten test results (positive/negative) will be presented by treatment group and visit. Additionally, an overall summary of subjects will be generated, cross-tabulating the baseline test result (positive/negative) with having at least one post-baseline test (positive/negative), separately for urine and stool tests.

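### The SAP's gluten-event table counts a positive test at the first-dose visit as an on-treatment event and leaves out the Week 2 tests

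*SAP*

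**What the plan says.** SAP 8.6.1.1 sets the rule: "Intercurrent events are events which occur after treatment initiation and may interfere with the analysis of the primary endpoint". It names two such events, prohibited medication and presence of gluten. The strategy for both is treatment policy: "Treatment policy strategy, i.e. all collected primary endpoint data is used regardless of intercurrent events".

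Gluten status is then assigned visit by visit from stool and urine tests. The table has seven rows: Month 0 at Visit 3, then Months 1 to 6 at Visits 5, 7, 9, 11, 13 and 15. The Month 1 condition for presence is "Stool or Urine gluten positive at Visit 5", with no reference to Visit 4. On timing the section says "Time (in weeks) from first dose to the first time observing the presence of gluten will also be captured for each subject", computed as the visit date minus the first double-blind dose date plus one, divided by seven.

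SAP 8.6.1.4 uses this status in a sensitivity analysis that is run if the evaluation of intercurrent events suggests a need. After a subject's first presence, observed data from later visits are kept only where the visit qualifies as absence. "Visits exhibiting the presence of gluten will be set to missing", and these are imputed from placebo subjects without gluten presence. Its worked examples use the same seven visits as the table.

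The schedule of activities and Protocol 8.1 both list stool and urine gluten tests at Visit 4, Week 2.

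**The concern.** Two features of the table do not fit the rest of the plan.

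- **Visit 3 is not after treatment initiation.** Urine is taken at the visit. Stool is normally taken the day before or during it, with three days' leeway either side. A positive result mainly describes diet before the first double-blind dose. Elsewhere the plan keeps the periods apart. Prohibited medication counts only from randomisation. SAP 8.6.3 summarises adherence by "cross-tabulating the baseline test result (positive/negative) with having at least one post-baseline test". The gluten subgroup in Protocol 9.4.2 counts post-baseline positives only.
- **Visit 4 is missing.** It is the first scheduled test visit after dosing began, and it anchors the Week 2 symptom score, which is one of the modelled time points. SAP 8.2.2.2 announces month-based windowing of gluten tests but gives no reason for dropping this visit.

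At stake is whether the counts and times of this intercurrent event describe exposure on treatment, and whether the gluten sensitivity analysis handles the right subjects and weeks.

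**Working it through.** The plan states no figure on this point, so there is none to reproduce.

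**Inputs.** The first double-blind dose is at Visit 3, Day 1 (SAP 8.2 and the schedule). Gluten tests from Visit 3 through Week 24 are scheduled at Visits 3, 4, 5, 7, 9, 11, 13 and 15. The table uses all of these except Visit 4. The primary model has 12 weekly scores, at Weeks 2, 4, ..., 24 (SAP 8.6.1.2).

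**Step 1, timing.** The SAP formula at scheduled days is (day − 1 + 1)/7.

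| Visit | Day | Weeks | In the table? |
|---|---|---|---|
| 3 | 1 | 0.14 | yes |
| 4 | 15 | 2.14 | no |
| 5 | 29 | 4.14 | yes |
| 7 | 57 | 8.14 | yes |

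A Visit 3 positive gets an event time of 0.14 weeks. A subject negative at Visit 3 whose first positive is at Visit 4 is dated to 4.14 weeks or later, or has no event if all later tests are negative.

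**Step 2, the 8.6.1.4 rule.** Take a subject positive at Visit 3 and negative at every later test. The table gives a status for Weeks 4, 8, 12, 16, 20 and 24 only. If Visit 3 is the first presence, Weeks 2, 6, 10, 14, 18 and 22 cannot show absence. Read literally, 6 of the 12 scores are then not used as observed, although no on-treatment test was positive. If Visit 3 is not an event, all 12 are used. The later sentence, which sets only visits with presence to missing, points the other way, and the text does not settle which governs.

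Now take a subject positive only at Visit 4. The subject counts as having no presence. The Week 2 score, from the seven days before Visit 4, is kept as observed.

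**Step 3, donors.** The comment in the 11.4 code limits donors to placebo subjects with no presence of gluten at all. A positive at Visit 3 alone removes a placebo subject. A positive at Visit 4 alone does not.

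**Step 4, illustration.** The documents give no positivity rate. Assume a constant, independent probability p of a positive at each test visit.

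- Expected Visit 3 positives among 220 subjects: 220 × p.
- Share of all first presences that fall at Visit 3, with seven table visits: p / (1 − (1 − p)^7).
- Share of subjects positive only at Visit 4 among the seven on-treatment tests, and so missed: p(1 − p)^6.

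| p | Visit 3 positives of 220 | First presences at Visit 3 | Positive only at Visit 4 |
|---|---|---|---|
| 0.05 | 11 | 17% | 3.7% |
| 0.10 | 22 | 19% | 5.3% |
| 0.20 | 44 | 25% | 5.2% |
| 0.30 | 66 | 33% | 3.5% |
| 0.50 | 110 | 50% | 0.8% |

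Under this assumption, replacing Visit 3 by Visit 4 leaves the expected number of subjects ever positive unchanged, because both schemes use seven tests: 30% at p = 0.05 and 79% at p = 0.20. What changes is which subjects are counted and when their event is dated. The totals would also move if diet changes after randomisation.

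**The case against.** The strongest reply is that little depends on this. The primary analysis uses all data whatever the gluten status. The gluten analysis is a conditional sensitivity analysis with no numerical trigger. Visit 3 positivity is balanced across arms in expectation. Month 0 can be read as a baseline label, with the general definition governing. Using only month-ending visits gives each month one test, whereas adding Visit 4 gives Month 1 two. Few subjects would be positive only at Visit 4.

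Most of this limits the consequences and leaves the defect in place. The baseline reading is sensible, but the SAP does not state it, and neither the timing formula nor 8.6.1.4 excludes Visit 3. One test per month is a possible reason for omitting Visit 4, but the SAP does not give it, and Week 2 has a modelled score and a scheduled test. It is also true that a Visit 3 stool sample may be taken after dosing, so not every Visit 3 positive is pre-treatment.

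A reader might infer more than the documents support:

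- *That a Visit 3 positive causes the baseline symptom score to be set to missing and imputed.* It does not. The diary windows start at Week 2, baseline is a separate seven-day average, and the MNAR statement in 11.4 covers only week2 to week24.
- *That the Visit 4 tests are never used.* SAP 8.6.3 tabulates gluten results by visit. The omission is confined to the intercurrent-event derivation.
- *That the counts decide whether the sensitivity analysis is run.* They inform a judgement; no threshold is set.

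**Conclusion.** The point holds within limits. The table conflicts with the SAP's own definition by including the first-dose visit, and it omits the first scheduled on-treatment tests. As written, pre-treatment exposure can be recorded as an event at 0.14 weeks. A first positive at Visit 4 is dated at least two weeks late or is missed. The consequences are confined to the event counts and timings, the 8.6.1.4 rule and the donor flag. The primary MMRM estimate does not change.

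The number of subjects affected cannot be known from the documents. The figures in Step 4 rest on an assumed positivity rate that is constant and independent across visits. Entry required detectable serology, which makes some Visit 3 positives plausible, but it is a different measure and gives no rate for the stool and urine tests. The SAP should be corrected because event times and the sensitivity analysis should refer to exposure after dosing.

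**What to change.** - In 8.6.1.1, label Visit 3 as baseline gluten status only and report it by arm.
- Start the event counts, time to first presence, the 8.6.1.4 rule and the 11.4 donor flag after the first double-blind dose. Where a Visit 3 stool sample was taken after dosing, classify it by its actual collection date.
- Add Visit 4 as a qualifying visit, or define Month 1 as any positive at Visit 4 or Visit 5.
- Align the 8.6.1.4 examples with these visits, and state how scores at weeks with no gluten test are treated after a first presence.

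The cost is SAP wording and a small amount of programming. The tests are already scheduled, so there is no added burden for subjects or sites. The drawback is that Month 1 then has two test opportunities where later months have one; a note to the monthly summary should say so.
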